This study is basically an extension study of our previous one (IRB 13-0566; Effects of the stimulation frequency of STN DBS on swallowing function in patients with Parkinson's disease, with publication in reference 20) but with a longer follow-up period (at least 6 months) in more patients and a full evaluation in each visit of maximum 2 visits in some patients.

Hypothesis:

The 60Hz stimulation would have persistent benefit in reducing the aspiration, FOG, other axial and motor symptoms in PD patients with bilateral STN DBS and medication refractory FOG at 130Hz stimulation over an extended period of at least months, even corrected for the potential carry-over effects between different test conditions.

Innovation:

This would be the first study on the chronic effect of the 60Hz stimulation on the dysphagia, FOG and other axial and motor symptoms in PD with bilateral STN DBS with medication refractory FOG at 130Hz stimulation.

Significance:

This study will provide a high evidence level and clinical recommendation on the chronic effect of the 60Hz stimulation on the treatment of the axial symptoms, particularly dysphagia and FOG, which are refractory to usual DBS setting and medications and associated with high morbidity and mortality in PD.

Aims:

Aim 1a: A study on the chronic effect (at least 6 months) of 60Hz stimulation on axial symptoms, including swallowing function and FOG, and parkinsonism to see whether the beneficial effect of 60Hz stimulation compared to 130Hz as revealed in our previous study²⁰, could be sustained in PD patients with bilateral STN DBS with medication refractory FOG at 130Hz.

Aim 1b: This study would also clarify the potential carry-over effect on stimulation (DBS 60Hz, DBS 130Hz, and DBS off, 30 min apart) on acute and chronic phase of the study to

enhance the quality of the study, and the level of evidence and recommendation in clinical applications.

Approach:

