Towards that aim, we will add 12 patients with medication refractory FOG at 130Hz of bilateral STN stimulation at medication on state for two visits of at least 6-months apart. We will plan to have 14 patients enrolled for visit 1, as 2 of them might drop off (or being unable to be on 60Hz due to worsening tremor) before visit 2 (estimated based on our previous study that 1 out of 7 patients could not be on 60Hz due to worsening tremor²⁰). The previous 6 study patients remaining on 60Hz stimulation after the completion of our previous study will be assessed again at visit 2 at least 12 months after the initial visit 1 once we get the IRB approval here.

We will then combine the data from these 14 newly added patients with the previous 7 patients at visit 1 to make 21 patients to complete the visit 1, and 18-20 (12 to 14 newly added patients plus previous 6) patients to complete a longer interval visit 2 of at least 6 months apart.

As our previous study²⁰, it will still be a randomized double-blind prospective cross-over study with medication on state but with 6-8 patients on each group of starting condition (60Hz vs 130Hz vs DBS off, 30 min apart) to allow us analyze the chronic effect and potential carry-over effect of stimulation between different conditions to increase the level of evidence, with 80% power to detect at least 25% difference at two-tail α level of 0.05, as estimated before²⁰. Aspiration frequency on MBS, difficulty in swallowing on questionnaire, FOG in SWS test and questionnaire, and axial subscore and UPDRS-III score will all be assessed accordingly under each DBS conditions as we did in our previous study²⁰, at both visit 1 and visit 2 of at least 6 months apart. The study will be finished in 2 years.

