Specifically, all the study patients will sign a written consent after the IEB approval. The study will be conducted at the Parkinson's Disease and Movement Disorder Center of Department of Neurology, Department of Radiology, Speech and Swallowing Section of Department of Surgery, and Center for Research Informatics at the University of Chicago from August 15, 2015 to March 15, 2017. Advanced PD patients with bilateral STN DBS placement and medication-refractory FOG at routinely used 130-Hz stimulation will be enrolled. The demographics of patients, such as gender, age at the study, disease duration, duration on bilateral STN DBS, and their Parkinson medications, electrode position and active contact positions and settings will all be recorded.

During visit, each patient will receive 3 routine modified barium swallow (MBS) studies in a single day under 3 different DBS frequency conditions (bilateral DBS 130 Hz, DBS 60 Hz, or DBS off) with their usual DBS voltage, pulse width, contact setting, and parkinsonian medication-on state regardless of the study stimulation frequency used. The study will be performed in a randomized and double-blind manner. The order of the DBS conditions will be assigned by the neurologist who will randomly pick up one of the 3 folded sheets with different conditions written on them and program the DBS accordingly, but will not be allowed to participate in any rating or evaluation. Neither the patients, nor the clinical rater, the pathologists for speech and swallowing, or the radiologist is aware of the DBS stimulation frequency condition. A single certified rater will rate all of the clinical scales and questionnaires, and a single swallowing team will conduct all MBS studies and the Penetration-

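### The folded-sheet draw, as described, does not assure the 6-8 patients per starting condition on which the carry-over analysis relies

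*Combined protocol and SAP*

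**What the plan says.** All references are to the combined protocol and SAP.

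- **Aims, Aim 1b.** Carry-over is a stated objective, in both the acute and the chronic phase: "This study would also clarify the potential carry-over effect on stimulation (DBS 60Hz, DBS 130Hz, and DBS off, 30 min apart".
- **Approach, group size.** The design is described as having "6-8 patients on each group of starting condition (60Hz vs 130Hz vs DBS off, 30 min apart", and the reason given is "to allow us analyze the chronic effect and potential carry-over effect of stimulation between different conditions".
- **Approach, sample size.** At visit 1 the plan is to "combine the data from these 14 newly added patients with the previous 7 patients at visit 1 to make 21 patients to complete the visit". At visit 2 it expects "18-20 (12 to 14 newly added patients plus previous 6) patients to complete a longer interval visit 2 of at least 6 months apart".
- **Approach, allocation.** The programming neurologist will "randomly pick up one of the 3 folded sheets with different conditions written on them and program the DBS accordingly", and takes no part in rating. The text does not say whether a sheet carries one condition or a whole order, or whether sheets go back between patients. It mentions no block, list, cap or reference to the orders the earlier 7 patients received.
- **Analysis.** The 60Hz-130Hz comparison is a paired t-test. No period, sequence or carry-over term is specified.

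**The concern.** The group size is presented as a feature of the design that enables an analysis. A simple draw for each patient gives that size only on average, and the realised split can be well away from it. Two things are at stake.

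- **Carry-over.** Its precision depends on how evenly the orders are spread. An uneven draw weakens an aim that already rests on about 20 patients.
- **The main 60Hz-130Hz contrast.** Each patient has three swallow studies in one day. If 60Hz happens to come before 130Hz much more often than after it, any trend over the day (fatigue, practice, medication wearing off) enters the paired difference, and the planned test does not remove it.

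**Working it through.** **Inputs.** From Approach: n=21 at visit 1 (14 new + 7 earlier), n=18-20 at visit 2, three starting conditions, target 6-8 in each. Assumption: each patient's first condition is an independent draw with probability 1/3. This holds whether the sheets carry single conditions or three complete orders with different first conditions.

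**1. The plan's own figure.** n/3 gives 18/3 = 6.0, 20/3 = 6.7 and 21/3 = 7.0. So 6-8 reproduces as an expected size.

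**2. Chance that all three groups hold 6-8.** Sum n!/(a! b! c!) / 3^n over the qualifying splits:

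| n | Qualifying splits | Calculation | Probability |
|---|---|---|---|
| 21 | 7/7/7; 6/7/8 (6 arrangements) | (399,072,960 + 6 × 349,188,840) / 10,460,353,203 | 23.8% |
| 20 | 6/7/7 (3); 6/6/8 (3) | (3 × 133,024,320 + 3 × 116,396,280) / 3,486,784,401 | 21.5% |
| 19 | 7/6/6 (3) | 3 × 46,558,512 / 1,162,261,467 | 12.0% |
| 18 | 6/6/6 only | 17,153,136 / 387,420,489 | 4.4% |

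**3. Visit 1 with the earlier 7 already fixed.** Their split is not stated, so it is varied, and only the 14 new patients are drawn. The chance is 31.6% for 3/2/2 (the best case), 27.0% for 3/3/1, 22.5% for 4/2/1, 12.8% for 5/1/1 and 1.2% for 7/0/0.

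**4. If the sheets are used up in threes.** The 14 new patients then split 5/5/4. Averaged over an unrestricted split of the earlier 7, the target is met at visit 1 in about 51% of cases. It is always met if the earlier split was 3/2/2, but in only one case in three if it was 4/2/1.

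**5. Chance that some group has 4 or fewer.** Same trinomial: 35.6% (n=21), 44.0% (n=20), 53.6% (n=19), 64.3% (n=18).

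**6. Effect on carry-over precision.** Simulation of 10,000 unrestricted draws of the six orders; model with patient, period, treatment and first-order carry-over. Carry-over was estimable in every draw. Among draws with a smallest starting group of 4 or fewer, the standard error relative to balanced orders was about 10% larger at the median, for both n=18 and n=21. At the 95th percentile it was about 26% larger (n=21) and about 29% larger (n=18).

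**7. 60Hz before or after 130Hz, at any position.** If all six orders are equally likely, three have 60Hz first of the two, so the count is Binomial(21, 1/2). P(14:7 or worse, either way) = 396,880 / 2^21 = 18.9%. To see what such a split does, suppose the outcome changes by δ per test period, with orders even within each side. The two conditions are on average (1 + 2 + 1)/3 = 4/3 periods apart, so the mean paired difference shifts by (14 − 7)/21 × 4/3 × δ = 0.44δ. The documents give no value for δ.

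**8. After the fix.** Balanced allocation gives 7/7/7, 7/7/6, 7/6/6 and 6/6/6 at n = 21, 20, 19 and 18, so the target is always met. At n=21, if the seven DBS-off starters split 4/3, 60Hz precedes 130Hz in 7 + 4 = 11 patients and follows it in 7 + 3 = 10.

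**The case against.** - **The draw is not called unrestricted.** True; that is inferred from a simple pick with no stated restriction. Sheets used up over successive patients would act as blocks of three. That would meet the target at visit 2 if every patient were drawn that way, and at visit 1 if the earlier 7 were split 3/2/2. The protocol says neither, and with an unknown earlier split the visit 1 chance is about 51%.
- **The range 6-8 may be only a planning average.** It does match n/3. But the text attaches an analysis to it, so it reads as a property of the design. If an average was meant, the wording should say so.
- **The 4% at n=18 is a threshold effect.** This stands: 7/6/5 counts as a miss and hardly matters. The precision figures are the better measure of harm.
- **A reader might infer that a small group makes carry-over impossible to estimate.** The check does not support that. Every patient contributes information on which condition preceded which, and the usual loss is modest.
- **A reader might infer that the 60Hz-130Hz contrast is biased.** It is a within-patient comparison with random order, so it is not biased in expectation. A particular draw distorts it only if there is a within-day trend, and the documents do not quantify one.
- **Balance alone does not deliver Aim 1b.** Correct: the Analysis section specifies no carry-over model. Balanced orders would still make any such model more precise.

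**Conclusion.** The point holds as a mismatch between a stated group size and a procedure that does not assure it. Under an independent one-in-three draw, the target is met in 24% of cases at n=21 (at most 32% once the earlier 7 are taken as fixed), 21% at n=20 and 4% at n=18. The cost is precision: typically about 10% on the carry-over standard error when a group has 4 or fewer patients, and 25-30% in bad draws.

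The 19% figure rests on all six orders being possible. It concerns 60Hz before or after 130Hz anywhere in the day. It should not be read as the imbalance between the 60Hz-starting and 130Hz-starting groups, for which a 2:1 or worse split has probability about 26% at n=21.

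The documents support neither a claim that Aim 1b is unachievable for this reason nor a claim that the primary comparison is invalid. The change is still worth making because it costs so little.

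**What to change.** 1. Replace the draw with a pre-prepared, randomly permuted list of the six possible orders, in numbered sealed sheets opened in sequence.
2. For visit 1, choose the 14 new orders so that, together with the earlier 7 patients' recorded starting conditions, the starting groups are 7/7/7. This is always reachable, since 7 patients cannot have used one starting condition more than 7 times. Make the six orders as equal as the earlier orders allow; 21/6 = 3.5, so ideally 3 or 4 of each.
3. Prepare a second balanced list for visit 2, covering 18-20 patients.
4. If the draw is kept, say whether sheets are returned between patients, and restate 6-8 as an expected average size and not as a design property.

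The cost is one prepared list per visit and a set of sealed sheets, with no extra visits or staff. It also requires retrieving the earlier patients' orders, which the protocol does not give. The drawback is that the last orders become predictable to the programming neurologist. That matters little, because this person already knows every setting and does no rating.

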Aspiration Scale ratings²⁵ to ensure consistency and quality of the evaluation. The MBS protocol consists of a standardized videofluorographic recording of oropharyngeal swallow in lateral and anterior-posterior views, and the anterior-posterior views. The subjects will be given radiopaque liquid, pureed contrast material, and solids coated in barium paste. The examinations will be recorded on the TIMS-DICOM digital medical recording system at high resolution of 30 frames per second. Frame-by-frame analysis will be used to evaluate oral, pharyngeal, laryngeal, and cricopharyngeal function. For the purposes of this study, special attention will be given to aspiration. Laryngeal penetration and aspiration events will be assessed using the Penetration-Aspiration Scale. The frequency of aspiration events will be calculated by adding the number of swallows within each DBS condition that generates a Penetration-Aspiration Scale. The swallowing questionnaire will be completed by each patient after the MBS study under each DBS condition²⁶. The parkinsonian motor, axial, and tremor symptoms as reflected by the Unified Parkinson's Disease Rating Scale, Part III (UPDRS-III) score, axial subscore (including gait, stance, posture, postural stability, and speech), and tremor subscore, respectively, and the FOG as reflected by a FOG questionnaire score,²⁷ and stand-walk-sit (SWS) test on FOG spell times and the time needed to finish the test (seconds) will also be assessed before the MBS study under each DBS condition. The patients will be on each DBS condition for at least 30 minutes before the study. The subjects will be video recorded while walking. The DBS condition producing the best gait function (least FOG, which was 60 Hz for all of our previous patients) will be continued for at least 6 months for the newly enrolled patients.

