Analysis: Changes in measurements between the 60Hz and 130Hz will be analyzed using paired t-test, with swallowing function (objective MBS study and subjective swallowing questionnaire) and FOG (objective SWS study and subjective questionnaire) as primary outcomes, and the rest (UPDRS-III score, axial subscore and tremor subscore) as the secondary outcomes in both acute visit1 and chronic visit 2 phase. Changes between other clinically relevant DBS conditions, including 60Hz vs DBS off, 130Hz vs DBS off, and 60Hz vs 60Hz follow-up (for >8 months on average) will also be explored and similarly analyzed with Bonferroni correction. A two-tailed alpha level of 0.05 will be taken as statistically significant for the comparisons.

Foreseeable difficulty or complications:

We don't anticipate any difficulty in conducting this study, as we had a successful similar study before²⁰, with IRB approval (University of Chicago). Medication refractory tremor could offset the 60Hz use as the tremor could be worse compared to 130Hz. However, most of the patient with axial symptoms has less tremor, and medication refractory tremor is even less. In the past, we had only 1 out of 7 patients who could not be on 60Hz stimulation due to the worsening of the tremor²⁰. No complication of aspiration pneumonia was found or reported before. The DBS condition used in the study will be the routine range of condition used in daily living without side effects. There is no alternative ways to conduct current study in order to get the important questions answered.

Pregnant woman, children or mentally retarded patients: None of them will be involved, as these advanced patients are all at the post-menopausal age. No children will be involved in

these advanced PD patient population. No mental retarded patient will be involved. All the patients will have the capacity to consent.

All study subjects will be paid \$200 for their participation in each visit study.

Research Environments:

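### At visit 2 only about one third of patients have 60Hz tested uninterrupted, yet the analysis pools their values with those of the 12-14 patients tested on 60Hz after other conditions

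*Combined protocol and SAP*

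**What the plan says.** Aim 1a (Aims section) asks whether the advantage of 60Hz over 130Hz is sustained over at least 6 months. Aim 1b asks about carry-over between conditions in both the acute and the chronic phase.

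Under Approach, new patients stay for at least 6 months on whichever condition gave the best gait, which was 60Hz in all previous patients. The earlier cohort returns at least 12 months after its first visit. Each visit then tests patients in a single day "under 3 different DBS frequency conditions (bilateral DBS 130 Hz, DBS 60 Hz, or DBS off". The order is set by a neurologist who will "randomly pick up one of the 3 folded sheets with different conditions written on them". On timing: "The patients will be on each DBS condition for at least 30 minutes before the study".

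The target allocation is "6-8 patients on each group of starting condition (60Hz vs 130Hz vs DBS off, 30 min apart", and the text says these groups exist so that the chronic and carry-over effects can be analysed. Expected numbers are "18-20 (12 to 14 newly added patients plus previous 6" at visit 2, after enrolment and pooling "to make 21 patients to complete the visit 1".

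The Analysis paragraph specifies paired t-tests of 60Hz against 130Hz at each visit. Among further comparisons, "60Hz vs 60Hz follow-up (for >8 months on average) will also be explored", with Bonferroni correction. It gives no term for order, period or preceding condition, and does not separate patients by starting condition. Nothing in the text puts 60Hz first at visit 2 or describes a rating before the first reprogramming of the day.

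**The concern.** Patients who have stayed on 60Hz arrive at visit 2 in exactly the state that Aim 1a is about. Those whose order begins with 60Hz are tested in that state. The rest are first moved to 130Hz, to DBS off, or to both, and are tested there before returning to 60Hz. The two groups therefore yield 60Hz values with different histories: one follows months of unbroken exposure, the other a fresh re-exposure of at least 30 minutes. The analysis treats them as the same quantity.

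The pooling is harmless if 60Hz has no slow component, or if any slow component survives the interruption. The documents establish neither. Their background section lists carry-over across conditions 30 minutes apart as an open question. It also cites a study in which gait improved at once on switching from 130Hz to 80Hz, with a benefit lasting less than 1 month. That study used another frequency and, by the plan's account, did not really study FOG, so it settles nothing for 60Hz. It does show why direction matters. If benefit fades at home and returns on re-exposure, pooling would overstate persistence. If benefit builds slowly and is lost on interruption, pooling would understate it.

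The comparison of 60Hz with its own follow-up is affected most directly. The visit-2 comparison of 60Hz with 130Hz uses the same 60Hz values, so it is affected too.

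**Working it through.** **Inputs.** From Approach: three conditions per visit, 6-8 patients per starting condition, 21 patients at visit 1, 18-20 at visit 2, at least 30 minutes on each condition before testing. From Analysis: paired t-tests only.

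**The plan's own figure.** Dividing N by 3 gives 21/3 = 7, 18/3 = 6 and 20/3 = 6.7 per starting condition. This agrees with the stated 6-8.

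**Share tested after an interruption.** Three conditions have 3! = 6 orders. 60Hz is first in 2, second in 2 and third in 2, so the expected share not starting on 60Hz is 4/6 = 66.7%. Requiring 6-8 in each of the three groups:

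| N at visit 2 | 60Hz first | Not 60Hz first | Share |
|---|---|---|---|
| 18 | 6 | 12 | 67% |
| 19 | 6-7 | 12-13 | 63-68% |
| 20 | 6-8 | 12-14 | 60-70% |

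The lower limit is 12. Taking 18 - 8 = 10 would leave 10 patients for two groups that need at least 6 each, so 18 patients can only split 6/6/6.

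These counts assume that the target allocation is met. The text describes a random draw without stating a balancing rule. Under unrestricted drawing, Binomial(N, 2/3), the 95% range is 8-16 of 18 or 9-17 of 20.

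**Length of interruption.** At least 30 minutes when 60Hz is second and at least 2 × 30 = 60 minutes when it is third, plus testing time in each case.

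**What pooling would show.** Let *f* be the fraction of any difference between the uninterrupted and the freshly re-exposed 60Hz state that survives the interruption. With one third of patients uninterrupted, the pooled mean shows 1/3 + (2/3)*f* of it:

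- *f* = 0: 1/3
- *f* = 0.5: 1/3 + 1/3 = 2/3
- *f* = 1: all of it, so no bias

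The documents give no basis for choosing *f*.

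**Precision of the 60Hz-first group.** The plan states 80% power for a 25% difference but gives no standard deviation, so that claim cannot be reproduced. As an illustration, take 80% power at the full visit-2 sample as given and solve for the standardised paired effect (noncentral t, two-sided 0.05):

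- N = 18: effect 0.70. In the 6 patients starting on 60Hz, power is about 29%.
- N = 20: effect 0.66. With 6, 7 or 8 such patients, power is about 26%, 31% or 37%.

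**The case against.** The strongest reply is that the design already contains what is needed. Patients who start visit 2 on 60Hz give a blinded, uninterrupted value on every outcome, including MBS, and the starting groups were set up for this purpose. That stands, and it means the gap lies in the analysis. A reader might infer that the arriving state is never measured. The documents do not support that, because for about one third of patients the first test of the day is that measurement.

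A second reply is that Aim 1a is tested by the blinded comparison of 60Hz with 130Hz within visit 2, while the comparison of 60Hz with its follow-up is only exploratory and, with random order at both visits, roughly alike in what precedes each test. This stands in part. Random order balances the test-day routine on average, but it does not make the interrupted values chronic, and the primary comparison uses those same values.

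Third, no passage shows that an effect built over months is lost after one or two short interruptions. This also stands. A reader might infer that the visit-2 60Hz value is mostly a 30-minute re-exposure. That goes beyond the text: 30 minutes is a minimum, and whether prior exposure still counts is unknown.

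Finally, a reader might extend the criticism to visit 1, where new patients arrive on 130Hz. The plan calls visit 1 the acute phase, so short exposure to 60Hz is what it intends to measure there.

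**Conclusion.** The point holds as a gap in the analysis. About two thirds of visit-2 patients (12-14 of 18-20) contribute a 60Hz value taken after an interruption, 6-8 contribute an uninterrupted one, and the planned t-tests do not distinguish them, although Aims 1a and 1b concern the chronic effect and carry-over.

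The counts rest on the stated 6-8 per starting condition being achieved at visit 2, and on patients actually arriving on 60Hz. Anyone whose retained condition was not 60Hz has no chronic 60Hz value in either group. The size and direction of any bias cannot be derived from the documents, and it may be zero. The finding is therefore not that the chronic result is wrong, but that the plan as written could not show whether it depends on the interruption.

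**What to change.** In the Analysis paragraph, for all outcomes including MBS:

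1. Report both visit-2 60Hz comparisons (against 130Hz, and against the visit-1 60Hz value) separately for patients who did and did not start visit 2 on 60Hz.
2. Fit a mixed model with a random patient effect and terms for condition, period and starting (or preceding) condition. Let the 60Hz effect differ by whether 60Hz came first; a main effect of starting condition alone would not return a 60Hz-first estimate.
3. Label the 60Hz-first estimate as the uninterrupted chronic value, restricted to patients who stayed on 60Hz. Present it as supportive, with confidence intervals and not a significance verdict.

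This uses data already planned, changes no stimulation setting and costs only analysis time. The downside is low precision with 6-8 patients. Within that group 60Hz also always comes first, so the split alone cannot separate condition from period. The model can, if period effects are assumed common to all starting groups.

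A rating on the home setting before the first reprogramming could be added as an optional, clearly labelled unblinded supplement. It would add a fourth assessment set to a day that already holds three MBS studies. It should not serve as the chronic 60Hz measure, because that would put an unblinded value in place of a blinded one.

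### The plan tests 60Hz against 130Hz separately at each visit, never estimates how much of the visit-1 difference is retained, and does not randomise the months-long setting

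*Combined protocol and SAP*

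**What the plan says.** - **Aim.** Aim 1a asks "whether the beneficial effect of 60Hz stimulation compared to 130Hz as revealed in our previous study" could be sustained over at least 6 months.
- **What is randomised.** The Approach states: "The order of the DBS conditions will be assigned by the neurologist who will randomly pick up one of the 3 folded sheets". This fixes the sequence of 60Hz, 130Hz and DBS off within a test day. On exposure it says: "The patients will be on each DBS condition for at least 30 minutes before the study".
- **What is not randomised.** For new patients, the setting used over the 6 months or more between visits follows from visit 1: "The DBS condition producing the best gait function (least FOG, which was 60 Hz for all of our previous patients) will be continued". The earlier cohort has its own rule: "The previous 6 study patients remaining on 60Hz stimulation after the completion of our previous study will be assessed again at visit 2".
- **Analysis.** "Changes in measurements between the 60Hz and 130Hz will be analyzed using paired t-test". Swallowing and freezing of gait (FOG) are primary and the remaining scores serve "as the secondary outcomes in both acute visit1 and chronic visit 2 phase". The only comparison that crosses visits is exploratory: "60Hz vs 60Hz follow-up (for >8 months on average) will also be explored".
- **Ambition.** The background calls for a formal randomised, blinded crossover study of chronic benefit, and the Significance paragraph expects a high level of evidence on the chronic effect.
- **Counts.** The Approach plans 21 patients at visit 1 (14 new, 7 earlier) and 18-20 at visit 2 (12-14 new, 6 earlier). The background says that 5 of the 7 earlier patients remain on 60Hz and gives reasons why the other 2 do not.

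**The concern.** Whether a benefit is sustained can be asked in two ways: is a difference still there at visit 2, and how does it compare in size with visit 1? The planned tests address the first. For the second, a reader would have only two separate p-values. A significant visit-2 test is compatible with full or partial retention, and a non-significant one can occur with no loss at all. The question is live, because the background cites a study in which a gait benefit at 80Hz lasted less than 1 month.

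The other risk is in interpretation. The trial is called randomised and its aim is chronic, so a positive visit-2 result could be reported as randomised evidence for months of 60Hz over months of 130Hz. For patients kept on 60Hz, the comparison is between a setting used for months and one used for at least 30 minutes.

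**Working it through.** **1. The plan's own figures.** Enrolment reproduces: 12/(1 − 1/7) = 14. Visit 1: 14 + 7 = 21. Visit 2: 12 + 6 = 18 to 14 + 6 = 20. With the background's 5 earlier patients: 12 + 5 = 17 to 14 + 5 = 19.

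The stated 80% power for a 25% difference (two-sided 0.05) cannot be reproduced, because no SD of the paired difference is given. Solving the paired-t power formula for that SD gives 25/0.701 = 35.7 points at n = 18 and 25/0.660 = 37.9 at n = 20. The claim therefore amounts to an effect of about 0.70 or 0.66 SD. Results below are in SDs of the within-patient 60Hz-130Hz difference, and 0.70 SD serves as an assumed effect.

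**2. What each contrast estimates.** Let D1 and D2 be a patient's 60Hz minus 130Hz difference at visits 1 and 2. The planned tests address mean D1 and mean D2. The change is

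D2 − D1 = (60Hz at visit 2 − 60Hz at visit 1) − (130Hz at visit 2 − 130Hz at visit 1).

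The exploratory 60Hz follow-up comparison is the first bracket alone, so it mixes loss of effect with disease progression. The second bracket is never used, although the Approach collects every outcome under each condition at both visits.

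**3. What a significant visit-2 test allows.** The smallest significant observed mean is t(n−1, 0.975)/√n. The largest observed loss still leaving visit 2 significant is 1 − threshold/visit-1 mean, for assumed visit-1 means of 0.75, 1.0 and 1.5 SD:

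| n | Threshold (SD) | Loss, 0.75 SD | Loss, 1.0 SD | Loss, 1.5 SD |
|---|---|---|---|---|
| 17 | 2.120/√17 = 0.514 | 31% | 49% | 66% |
| 18 | 2.110/√18 = 0.497 | 34% | 50% | 67% |
| 20 | 2.093/√20 = 0.468 | 38% | 53% | 69% |

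**4. What a non-significant visit-2 test allows.** Simulation with 100,000 trials per setting, 21 patients at visit 1 and a true difference of 0.70 SD at both visits. The share of trials with visit 1 significant and visit 2 not, for assumed between-visit correlations r of 0.3 / 0.5 / 0.7:

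- n = 17: 17.7% / 16.1% / 14.3%
- n = 18: 15.4% / 14.2% / 12.0%
- n = 20: 11.7% / 10.5% / 8.5%

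So with nothing lost, about 8% to 18% of such trials would look like loss.

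**5. Precision of the missing estimate.** With equal SDs at both visits, the SD of D2 − D1 is √(2(1 − r)), and the 95% CI half-width is t(n−1, 0.975) × √(2(1 − r)/n). Example, n = 18 and r = 0.5: 2.110 × √(1/18) = 0.50. Power is for losing half of 0.70 SD, that is 0.35 SD (noncentral t).

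| n | Half-width (SD), r = 0.3 / 0.5 / 0.7 | Power, r = 0.3 / 0.5 / 0.7 |
|---|---|---|
| 17 | 0.61 / 0.51 / 0.40 | 21% / 27% / 42% |
| 18 | 0.59 / 0.50 / 0.39 | 22% / 29% / 44% |
| 20 | 0.55 / 0.47 / 0.36 | 24% / 32% / 48% |

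**6. Continuation on 60Hz.** Exact 95% CIs if k of 21 remain: 17, 81% (58%-95%); 18, 86% (64%-97%); 19, 90% (70%-99%); 20, 95% (76%-99.9%).

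**The case against.** **The visit-2 test already answers Aim 1a.** It asks whether 60Hz still does better than 130Hz after at least 6 months, which is an ordinary reading of a sustained benefit. This stands. A reader might infer that the planned tests leave the aim unanswered, but the documents do not support that: they leave the amount retained unestimated.

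**No long-term 130Hz comparison was promised.** This also stands. A reader might infer that the trial fails for want of a randomised long-term 130Hz group, but no passage states an aim of comparing months on one frequency with months on the other. What remains is a limit on the conclusion, which matters given the background's language.

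**The change estimate would not settle persistence.** Largely right. Every half-width in step 5 exceeds 0.35 SD, so an observed change of zero would not exclude losing half of a 0.70 SD effect. The estimate is also not pure. New patients enter with FOG at the routinely used 130Hz. If that is their habitual setting, visit 1 sets habitual 130Hz against brief 60Hz, and visit 2 reverses this for those kept on 60Hz. Regression to the mean, and progression that differs by frequency, can add to any apparent change. The estimate should therefore supplement the visit-2 test and not replace it.

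**Selection is not shown to bias anything.** Recalling earlier patients who remain on 60Hz might suggest an inflated visit-2 result. The documents do not establish that: all 14 new patients may attend, and the two earlier departures were for tremor and an unrelated infection. The size is unknown and may be nil.

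**Conclusion.** The concern holds in a limited form. The visit-2 test can show that a short-term difference is still present. It cannot show how much of the visit-1 difference is retained, and the exploratory 60Hz follow-up comparison does not fill the gap. Randomisation covers the order within a day and not the chronic exposure, so the trial cannot give randomised evidence that months on 60Hz beat months on 130Hz.

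In size, observed losses of roughly a third to two thirds could still leave visit 2 significant (assumed visit-1 means of 0.75 to 1.5 SD), and a fully retained 0.70 SD effect would look lost in about 8% to 18% of trials. These are illustrations: the plan gives no SD, and the effects, the correlations of 0.3 to 0.7 and equal SDs at the two visits are assumptions. That the retained share is not estimated, and that the chronic setting is not randomised, depend on none of them. The 5-against-6 conflict is textual and shifts the visit-2 total by one. The data remain usable, and this should be fixed before analysis.

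**What to change.** 1. Keep the visit-2 paired test. Add, as a key supplementary estimate, the within-patient change (visit 2 minus visit 1) in the 60Hz-130Hz difference with its 95% CI. Use patients kept on 60Hz with both visits, and also all patients with both visits if these sets differ. State in advance that the CI will be wide, that a non-significant change does not prove persistence, and that the change may also reflect regression to the mean, a different habitual setting before each visit, and progression that differs by frequency.
2. Limit the chronic conclusion to this: the short-term 60Hz-130Hz difference is still present after at least 6 months in patients kept on 60Hz.
3. Report, out of all enrolled patients, how many remained on 60Hz at visit 2, with an exact 95% CI and the reasons for leaving. Keep this apart from efficacy.
4. Reconcile the background (5 of 7 remaining on 60Hz) with the Approach (6), and correct the visit-2 total if needed.

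**Cost.** One further analysis of data already planned, plus wording. No added visits or barium studies, and no change to anyone's stimulation. The price is a wide interval and a more modest chronic conclusion.
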